Specific Aim 2: To determine if a ventilator strategy in children with ARDS that promotes spontaneous breathing and physiologic levels of patient effort results in different rates and subtypes of PVA, and if PVA mediates the relationship between this intervention and clinical or mechanistic outcomes. **Hypothesis:** (a) REDvent intervention patients will have a different distribution of PVA subtypes than usual care patients which will partially mediate the relationship between REDvent intervention and outcome. (b) PVA subtypes which lead to DC breaths will be associated with clinical and mechanistic outcomes. **Study Design:** Secondary analysis of waveforms and clinical data from the REDvent clinical trial.

Preliminary Data

The relationship between PVA and clinical outcomes is complex because PVA is more likely to occur in patients with more spontaneous breathing. A conventional ventilator management strategy for patients with ARDS promotes controlled ventilation with high degrees of sedation or neuromuscular blockade with low rates of spontaneous breathing early during ventilation, followed by spontaneous breathing

[figure not shown]

Figure 5:
Conceptual model for Aim 2

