when evaluating for readiness for ventilator liberation.²¹ These patients may have lower rates of PVA because they are not permitted to breathe spontaneously until the ARDS is largely resolved, but they may have longer length of ventilation because of the lack of spontaneous breathing. A balanced lung and diaphragm protective strategy, like what is being tested in the REDvent trial, promotes spontaneous breathing earlier during ventilation. We hypothesize that this will result in shorter time on ventilation by reducing the rates of over and under assistance myotrauma (VIDD) as well as more lung protection (VILI).^{22,24,45} However, earlier spontaneous breathing may result in a higher overall rate of PVA in REDvent versus control patients, but a different distribution of PVA subtypes. Because REDvent targets physiologic levels of respiratory effort, it is likely that the under-assistance related causes of PVA which lead to double cycling (flow undershoot/premature termination) will occur less frequently. However, the lung protective component of REDvent frequently uses a higher ventilator rate than usual care, which may make Reverse Trigger more common, with double cycling. **It is therefore highly plausible that PVA frequency and subtype may mediate the relationship between REDvent intervention and outcome (Figure 5).** It is therefore important to understand when the benefits of spontaneous breathing related to prevention of diaphragm atrophy are outweighed by any additional risks related to PVA. The analytic framework must consider these potentially competing principles. Adult data confirms associations between PVA (and its subtypes) and adverse clinical outcomes.¹²⁻¹⁶ Nevertheless, human studies have not confirmed mechanistic pathways involved, although pre-clinical data support these proposed mechanisms of injury.⁶⁴⁻⁶⁷ While this study will primarily establish associations, a mediation approach (see below) to the analysis allows for causal inference and specifically leverages the **randomized** nature of the REDvent trial. To decouple these effects, when analyzing the relationship between PVA variables and length of ventilation, we stratify or control for the time to spontaneous breathing.

[figure not shown]

Figure 6: Relationship between Asynchrony index and sarcomere disruption of the diaphragm in a rabbit model for PVA

sarcomere disruption and atrophy result in functional impairments seen in VIDD, albeit with different mechanisms.

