Methods and Analysis Hypothesis B: Here we seek to understand which PVA subtypes and frequency are independently associated with clinical or mechanistic outcomes. The primary clinical outcome is length of mechanical ventilation after the first day of spontaneous breathing. This is the primary outcome because the relationship between PVA rates and length of ventilation is confounded by time to first day of spontaneous breathing, as discussed above. Patients who have highly controlled ventilation without spontaneous breathing for several days inherently cannot develop PVA, as there is no significant patient effort. Secondary short-term clinical outcomes include length of mechanical ventilation, length of the weaning phase of mechanical ventilation (time from first spontaneous breathing trial until extubation), 90-day mortality and re-intubation. Secondary longer-term clinical outcomes include pulmonary function, neurocognitive function, and health related quality of life for the 2 years after ICU discharge amongst survivors. Mechanistic outcomes will focus on pathways of injury hypothesized to be associated with PVA, summarized by PVA subtype in Table 2.

PVA Subtype	Mechanistic Pathway	Variables to be considered
“Inadequate Support”: Flow Undershoot or Premature Cycling	VILI, VIDD (Over-use)	Transpulmonary Pressure, Tidal Volume, Resolution of Organ Dysfunction, Resolution of Lung Injury, PiMax, Diaphragm Thickness
Reverse Trigger	VIDD (Eccentric Contraction), Delirium, Excess Sedation	PiMax, Diaphragm Thickness, Cornell Assessment of Pediatric Delirium, Cumulative Dose of Sedatives and Opioids
Double Cycle (All causes)	VILI	Transpulmonary Pressure, Tidal Volume, Resolution of Organ Dysfunction, Resolution of Lung Injury
Asynchrony Index (All PVA)	Delirium, Excess Sedation	Cornell Assessment of Pediatric Delirium, State Behavioral Scale, FLACC Score, Cumulative Dose of Sedatives and Opioids

Table 2: Analytic Plan with PVA variable of interest, mediation variables to be investigated, and hypothesized mechanistic pathway.

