Univariable analysis will focus on the relationship between the PVA variables above and clinical and mechanistic outcomes. Nearly all the variables of interest are continuous, so analyses will focus on strength of association and dose response. Nonparametric or parametric correlations will explore the relationships between continuous variables. The primary clinical outcome of length of ventilation after the first day of spontaneous breathing will be modelled with a competing risk regression to look at time to extubation against the competing risk of death. This type of model is necessary rather than traditional survival analysis or linear regression because both death and prolonged ventilation are undesired outcomes, and some proportion of children (likely 5-10%) will die even after the first day of spontaneous breathing. We have successfully used this framework in previous investigations.⁶⁸⁻⁷² We will then add in variables which may confound the relationship between PVA and clinical outcomes including demographic factors (age, co-morbidities), severity of initial lung injury, diagnostic data and medications. Similar analyses will be repeated all clinical and mechanistic outcomes. For mechanistic analysis (table 2), within each of the proposed mechanisms (VILI, VIDD, Delirium), the variable with the strongest association with PVA (or its subtype) will be included as the outcome variable.

Specific Aim 3) To develop and test a clinical decision support system using machine learning techniques to automatically identify common forms of PVA in children.

Hypothesis: (a) Machine learning models using waveforms available on all mechanical ventilators will accurately identify PVA subtypes compared to gold standard annotations which include measures of neural drive. (b) Algorithms can be optimized for high sensitivity and low false alert rates to identify children with frequent PVA.

Preliminary Data

Machine learning methods can detect DC breaths and the PVA subtypes leading to DC. We have been developing a machine learning framework using Spectral Analysis with a Convolutional Neural Network to detect PVA subtypes. Details about the methods used (and intend to employ here) are described below. Preliminary models were trained on 34, validated on 13 and tested on 18 patients from the REDvent dataset.

[figure not shown]

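### The confounders named for the Hypothesis B asynchrony models do not include randomised allocation, which confounds the estimates for those subtypes and outcomes that REDvent itself affects

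*Combined protocol and SAP*

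**What the plan says.** Hypothesis B (protocol Section H, Aim 2, Methods and Analysis Hypothesis B) sets out to learn "which PVA subtypes and frequency are independently associated with clinical or mechanistic outcomes". Its primary clinical outcome is length of ventilation counted from the first day of spontaneous breathing, analysed by competing-risk regression with death as the competing event. On adjustment it says "We will then add in variables which may confound the relationship between PVA and clinical outcomes including" and then lists "demographic factors (age, co-morbidities), severity of initial lung injury, diagnostic data and medications". The same approach is to be repeated for all clinical and mechanistic outcomes.

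The Aim 2 preliminary data add one more adjustment. When PVA is related to length of ventilation, time to spontaneous breathing is stratified on or controlled for.

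On what REDvent does, Aim 2 is explicit:

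- In general, "REDvent intervention patients will have a different distribution of PVA subtypes than usual care patients".
- On reverse trigger, "the lung protective component of REDvent frequently uses a higher ventilator rate than usual care, which may make Reverse Trigger more common".
- On under-assistance, the forms named are "flow undershoot/premature termination) will occur less frequently".
- On length of ventilation, "We hypothesize that this will result in shorter time on ventilation".

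Protocol section A3 also expects REDvent to reduce respiratory muscle weakness.

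Arm and PVA share a model in Hypothesis A, the mediation analysis. There a subtype enters only if it differs between arms, and what is read is the change in the REDvent coefficient.

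**The concern.** Allocation is fixed before any asynchrony is recorded. If it moves both a PVA subtype and the outcome, it is a common cause of the two. A pooled model without it then credits the subtype with part of REDvent's effect. A subtype that REDvent makes more common would look less harmful than it is, and one that REDvent makes rarer would look more harmful. Because allocation precedes PVA, it cannot lie on the path from PVA to outcome, so adjusting for it removes none of the PVA effect.

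The question reaches beyond length of ventilation. The mechanistic outcomes in Section H Table 2 include PiMax, diaphragm thickness and tidal volume. REDvent is meant to preserve muscle strength, and its decision tool recommends ventilator pressure or tidal volume (protocol D.3.2). Within each mechanism the plan takes forward the variable most strongly associated with PVA, which can favour the one most confounded by arm.

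**Working it through.** **Plan figures.** Hypothesis B states no power or sample size, so there is no figure to reproduce. The 0.84 given in Aim 2 belongs to the Hypothesis A mediation analysis, and nothing below rests on it. From N = 235 and two partial correlations of 0.3 at two-sided 0.05, the Sobel and Aroian approximations give 0.89 to 0.92 and joint significance 0.99. The plan states neither test nor alpha, so no error is claimed.

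**Inputs from the documents.** 235 children and a median of 4 days from first spontaneous breathing to extubation (Section H, Aim 2, sample size). Deaths after that day 5-10% (Hypothesis B); about 7% simulated. Allocation 1:1 (SAP July 2024).

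**Assumptions.**
- g, the log HR of REDvent for extubation: log 1.4 to log 1.5. This borrows the design values for weaning duration (protocol D.6.4.1). No value is given for ventilation after first spontaneous breathing.
- a, the shift in a PVA subtype between arms, in SD: 0 to 0.75 for reverse trigger and -0.5 for flow undershoot. The documents give no size.
- Two-sided alpha 0.05, as in the main trial. None is stated for the asynchrony aims.

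**Linear approximation.** For a 1:1 arm left out of the model, the bias on the log HR per SD of PVA is

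bias = g × (a/4) / (1 + a²/4).

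| Arm HR | a (SD) | Bias |
|---|---|---|
| 1.4 | 0.25 | 0.336 × 0.0625 / 1.0156 = 0.021 |
| 1.4 | 0.50 | 0.336 × 0.125 / 1.0625 = 0.040 |
| 1.5 | 0.50 | 0.405 × 0.125 / 1.0625 = 0.048 |
| 1.5 | 0.75 | 0.405 × 0.1875 / 1.1406 = 0.067 |

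A positive sign means toward less harm. The bias is zero if a = 0 or g = 0.

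**Simulation.** Fine-Gray-type regression with the inputs above, censoring at 28 days, 600 replicates per cell. The Monte Carlo SE is about 0.02 on a power near 0.6 and 0.01 on a rate near 7%. An HR below 1 per SD of PVA means slower extubation.

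Power to show harm, true HR 0.80 per SD:

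| Arm HR | a (SD) | Without arm | With arm |
|---|---|---|---|
| 1.0 | 0.50 | 0.79 | 0.77 |
| 1.4 | 0 | 0.72 | 0.73 |
| 1.2 | 0.50 | 0.66 | 0.73 |
| 1.4 | 0.25 | 0.64 | 0.72 |
| 1.4 | 0.50 | 0.58 | 0.74 |
| 1.4 | 0.75 | 0.52 | 0.75 |
| 1.5 | 0.75 | 0.47 | 0.72 |

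The first two rows are the controls: with no arm effect on the outcome, or none on the subtype, omission does no damage.

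Other results at arm HR 1.4:
- Estimated HR at a = 0.5, true 0.80: 0.86 without the arm, 0.83 with it. The gap between 0.80 and 0.83 is not due to the omission; it is also there with no arm effect at all (0.835).
- True HR 0.90, a = 0.5: power 0.11 against 0.24 (0.235 before rounding).
- No true effect: false protective findings 7.0% against 2.3% at a = 0.5, and 12.3% against 2.5% at a = 0.75.
- Flow undershoot, a = -0.5, no true effect: false harm 6.8% against 2.7%.
- SE at a = 0.5, no true effect: 0.067 without the arm, 0.069 with it.

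**The case against.** **The list is open.** It is introduced by a word that signals examples, and allocation meets the stated criterion of a possible confounder. A reader might infer that the plan excludes the arm; the text does not say so. This stands. Still, allocation is the one confounder that the plan's own hypotheses identify, and leaving it to the analyst's choice is avoidable.

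**Time to spontaneous breathing is already handled.** Starting the clock at the first spontaneous breath and controlling for time to it should remove part of REDvent's path, so the arm effect that remains may be smaller than assumed. That stands too. But this adjustment is stated only for length of ventilation. It does not block the ventilator-rate route to reverse trigger. REDvent also goes on acting after spontaneous breathing begins, through the effort rules in D.3.2 and the pressure-support titration in D.3.7.

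**Hypothesis A already puts arm and PVA together.** It does for subtypes that differ between arms, which are the ones at risk. Its Mann-Whitney screen would rarely miss a large shift. With about 117.5 per arm the SE of a difference is √(2/117.5) = 0.130 SD. With efficiency 0.955, a 0.5 SD shift gives 0.5 × √0.955 / 0.130 = 3.75, so power is about 0.96; a 0.3 SD shift gives about 0.6. But Hypothesis A reads the arm coefficient. The PVA coefficients behind the independent-association conclusions come from Hypothesis B.

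**The size could be pushed up.** Taking the pilot weaning ratio, 4/2.2 = 1.82, as a hazard ratio together with a 1.0 SD shift gives a two-sided false-positive rate of 0.21. The documents do not support that: 1.82 is a ratio of pilot weaning days against historical controls, and the 1.0 SD shift has no source. The pilot ratio for length of ventilation is 8.4/6.5 = 1.29, with p = 0.36.

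**Conclusion.** The point holds for subtypes and outcomes that REDvent affects. Run with the named covariates, Hypothesis B would bias reverse trigger toward no harm, if REDvent does make it more common, and flow undershoot toward harm. A reader might infer that every PVA-outcome estimate is confounded. That does not follow: bias needs an arm effect on both sides, the plan says only that reverse trigger may become more common, and the final SAP (Table 1, ventilator-free days) expects no treatment effect on death, so the 90-day mortality estimates are unaffected on the plan's own terms.

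The size is modest: about 0.04 on the log HR per SD, with a power loss of 16 points (0.74 - 0.58), at arm HR 1.4 and a 0.5 SD shift. Both inputs are assumptions. The effect goes to zero if either arm effect is absent, and shrinks to the extent that time to spontaneous breathing absorbs the arm effect. This is a nearly free improvement to a secondary, associational analysis; it does not touch the randomised comparisons.

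**What to change.** In Section H, Methods and Analysis Hypothesis B, state that:

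- all adjusted models, clinical and mechanistic, include acute-phase allocation as a covariate or stratum, in addition to time to spontaneous breathing where length of ventilation is the outcome;
- models of weaning-phase outcomes also include weaning-phase allocation for the children who underwent that randomisation;
- conclusions about independent association are drawn from these models.

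A PVA-by-arm term or within-arm estimates would serve as a sensitivity analysis.

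The cost is one sentence and one or two parameters. Allocation is already recorded, and the simulated SE rises only from 0.067 to 0.069.

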The REDvent study will evaluate whether the REDvent intervention results in improvement in length of mechanical ventilation (clinical outcome), as well as mechanistic outcomes (PiMax and Diaphragm Atrophy). The impact of REDvent group on time to event variables (i.e. length of ventilation) will be analyzed with competing risk regression (competing risk of death), continuous outcomes (i.e. PiMax) with linear regression, and dichotomous variables (i.e. mortality) with logistic regression. In mediation analysis we will add the PVA subtypes which are different between REDvent and control patients to multivariable models. The PVA subtype will be considered a mediator if it changes the parameter estimate of the REDvent intervention by more than 20%. If the PVA subtype significantly strengthens the association between REDvent intervention and outcomes, then therapeutic trials which seek to decrease that PVA subtype may be beneficial (e.g Reverse Trigger). In contrast, if controlling for PVA subtype weakens the association between REDvent and outcome, then strategies to mitigate that type of PVA may be more harmful (e.g. Flow Undershoot). This approach allows us to simultaneously evaluate the potential benefits of a lung and diaphragm protective strategy and understand the extent to which PVA subtypes which are different between intervention and control groups affects outcomes. This type of causal inference analysis is possible because of the randomized nature of the REDvent trial in which the intervention is likely to affect PVA rates and subtypes.

Sample Size and Power: We anticipate 235 patients available for analysis, with a median time from first day of spontaneous breathing to extubation of 4 days. Using a proposed mediation analysis with a conservative estimate for a partial “r” of 0.3 of the PVA variable with the mediator outcome, a partial “r” of 0.3 for the mediator outcome with the clinical variable, then we would have a power of 0.84 to detect the overall effect estimate in the mediation model.

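### Asynchrony Aim 2, Hypothesis B: picking each mechanism's outcome by its observed association with PVA biases the mechanistic estimates and p-values

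*Combined protocol and SAP*

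**What the plan says.** Hypothesis (b) of Asynchrony Specific Aim 2 states that "PVA subtypes which lead to DC breaths will be associated with clinical and mechanistic outcomes". The study design for the aim is given as "Secondary analysis of waveforms and clinical data from the REDvent clinical trial", and the sample-size paragraph under Hypothesis A says "We anticipate 235 patients available for analysis".

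Table 2, under Methods and Analysis Hypothesis B, lists candidate variables for each PVA (patient-ventilator asynchrony) subtype and pathway:

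- Double-cycle row, whose only pathway is ventilator-induced lung injury (VILI): "Transpulmonary Pressure, Tidal Volume, Resolution of Organ Dysfunction, Resolution of Lung Injury".
- Diaphragm dysfunction (VIDD), in the inadequate-support and reverse-trigger rows: "PiMax, Diaphragm Thickness".
- Asynchrony-index row, with delirium and excess sedation as joint pathways: "Cornell Assessment of Pediatric Delirium, State Behavioral Scale, FLACC Score, Cumulative Dose of Sedatives and Opioids".

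The text after Table 2 begins with univariable associations between PVA and these outcomes, then adds confounders. It ends by stating that, for the mechanistic analysis, the choice is made inside each of three mechanisms (VILI, VIDD and delirium) and that "the variable with the strongest association with PVA (or its subtype) will be included as the outcome variable".

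No significance threshold, data split, ranking of outcomes or correction for selection is given for this step. The final SAP (July 2024) plans no multiplicity adjustment for the trial's secondary outcomes. A test set used only once appears in Asynchrony Aim 3, for the machine-learning models, but not in Aim 2.

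**The concern.** The candidate with the largest observed association is partly the one that chance favoured most. If that same association is then reported from the same patients as the mechanism's result, its estimate is too large on average, and its p-value no longer has its nominal meaning. The p-value refers to one outcome fixed in advance, while the procedure takes the best of several.

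What is at stake is the mechanistic half of Hypothesis (b). Double cycling is the section's stated focus, and in Table 2 it is linked to lung injury only, the mechanism with the clearest four-candidate pool. Links that look stronger than they are could then influence which forms of asynchrony are targeted in later trials.

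**Working it through.** The plan gives no error rate for this step, so there is no stated figure to reproduce.

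**Inputs**
- Candidates per mechanism (Table 2): k = 4 for VILI and k = 2 for VIDD. For delirium, k = 1 if the Cornell score is the only candidate, k = 4 if the whole asynchrony-index row is pooled, and k = 5 if sedative and opioid doses also count separately. Table 2 does not say which applies.
- Sample size: n = 235 (Aim 2, Hypothesis A).
- Threshold: two-sided 0.05. This is an assumption, borrowed from the SAP's power analysis for the trial's primary outcome.
- Correlation among candidates: not given, so an assumed range of 0 to 0.9 is used. For the VIDD pair, protocol D.6.4.2 expects aPiMax and diaphragm atrophy to be highly correlated.

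**Chance that the selected candidate has p<0.05 when none is associated with PVA**

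With independent candidates the chance is 1 − (1 − 0.05)^k:
- k = 1: 0.050
- k = 2: 1 − 0.95² = 0.0975
- k = 4: 1 − 0.95⁴ = 0.1855
- k = 5: 1 − 0.95⁵ = 0.2262

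Under any dependence the chance cannot exceed k × 0.05, which is 0.10 for two candidates and 0.20 for four.

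For correlated candidates, a simulation (n = 235, 20,000 replicates, equal correlation ρ) took the largest absolute univariable correlation and tested it on the same data:

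| ρ | k = 4 | k = 2 |
|---|---|---|
| 0 | 0.186 | 0.097 |
| 0.3 | 0.179 | 0.096 |
| 0.5 | 0.152 | 0.090 |
| 0.7 | 0.131 | 0.083 |
| 0.9 | 0.094 | 0.072 |

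Adjusting the final test for five covariates unrelated to outcome changes little (0.187 for k = 4, ρ = 0). If the covariates explain 30% of outcome variance, the adjusted test gives 0.156 at ρ = 0 and 0.144 at ρ = 0.3, for k = 4.

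**Size of the estimate when nothing is associated**

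For one pre-named outcome, the expected absolute correlation is about √(2/π) / √(n − 1) = 0.798 / √234 = 0.052. For the best of four, simulation gives 0.096 at ρ = 0, 0.090 at ρ = 0.5 and 0.072 at ρ = 0.9.

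These figures are for one PVA variable at a time. If the selection also ranged over PVA subtypes, which the rule's wording leaves open, the pool would be larger. That is not counted here.

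**The case against.** Five points can be made for the plan.

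1. **Reach.** Hypothesis B has a primary clinical outcome fixed in advance: length of ventilation after the first day of spontaneous breathing. The selection rule does not touch it, the trial's primary outcome, or any outcome in SAP Table 1. This stands, and it confines the point to the mechanistic outcomes of an ancillary analysis.
2. **Visibility.** The same paragraph plans univariable analyses of the mechanistic outcomes and says similar analyses are repeated for all outcomes. If all are reported, a reader can see what the selected variable was chosen from. This mitigates the problem, but the selected variable's own estimate and p-value remain uncorrected.
3. **Purpose.** The section stresses strength of association and dose response, says the study will mainly establish associations, and sets no threshold. The 5% benchmark is therefore an assumption. Selection still inflates the estimate with no threshold at all.
4. **Correlation.** Related candidates reduce the inflation. For VIDD the documents themselves expect high correlation. For VILI, the section's preliminary data say that double cycling produces both very high tidal volumes and high transpulmonary pressure, so correlation is plausible there too. This stands and is why a range is shown.
5. **Delirium.** If the Cornell score is the only candidate, nothing is selected.

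A reader might infer from the four-candidate case that the rule inflates false positives nearly fourfold in general (0.1855 / 0.05 = 3.7). The documents do not support that. The figure needs four mutually independent candidates and an assumed 0.05 threshold. It is a near-maximum for a four-candidate pool, and VILI is the only mechanism that clearly has one.

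**Conclusion.** The point holds as a limited one. As written, the rule selects and then estimates the same association in the same patients, so the mechanistic results of Hypothesis B are biased by selection.

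Under the assumptions above, a four-candidate mechanism gives p<0.05 by chance about 9-19% of the time (1.9 to 3.7 times nominal). VIDD gives 7-10%, probably nearer 7% given the high correlation the protocol expects. Delirium ranges from no inflation upward, according to how Table 2 is read. With no true association and 235 patients, the typical reported correlation would be 0.07-0.10 for the best of four, against 0.05 for an outcome named in advance.

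It would go too far to conclude that Hypothesis B as a whole, or any trial endpoint, is compromised: the outcomes outside the mechanistic part are named in advance and are not chosen by this rule. This is a desirable correction to an ancillary analysis rather than a threat to the trial's conclusions.

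**What to change.** Before the analysis is run, do one of the following.

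- **Name one outcome per mechanism in Table 2.** For VIDD, aPiMax is the natural choice, because protocol C.3.2 already makes it the primary physiologic outcome. For delirium, use the Cornell score. For VILI, the investigators should choose one of the four listed variables, since this is where the inflation is clearest. Report the remaining candidates as supportive. The error rate returns to 5% per mechanism.
- **Keep the selection but correct for it.** Judge the selected association with a max-T permutation p-value over all candidates in the mechanism, or against 0.05/k (0.05/4 = 0.0125 for four candidates, 0.05/2 = 0.025 for two). Define which variables belong to delirium, and report every candidate's estimate. This corrects the p-value only, so the selected estimate should be described as the largest of k.

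The first option costs one added column in Table 2, and the pre-named variable may turn out not to be the most responsive. The second costs a somewhat stricter threshold. If max-T is used with adjusted models, the permutation scheme also has to be specified. Neither option needs new data.
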